6.6 Treatment compliance

The administration of all medication (including investigational products) must be recorded in the appropriate sections of the Case Report Forms.

Drug accountability will be performed at Visits 3 and 4 to assess compliance. Compliance of $\leq 80\%$ will be considered unacceptable.

6.6.1 Accountability

The study drug provided for this study will be used only as directed in the study protocol.

The study personnel will account for all drugs dispensed and returned.

Site personnel will account for all unused drugs and for appropriate destruction. Certificates of delivery, destruction and return must be signed.

7. COLLECTION OF STUDY VARIABLES

7.1 Recording of data

The investigator will ensure that all data collected in the study are provided to AstraZeneca. He/she ensures the accuracy, completeness, legibility and timeliness of the data recorded in the appropriate sections of the paper Case Report Form and according to any instructions provided.

Patients will be asked to complete their Bronkotest[®] diary card on a daily basis, and will be required to bring it along to each scheduled clinic study visit where study staff at site will review it for completeness and provide feedback and guidance on its completion where necessary.

7.2 Screening and demography procedures

Investigators should refer to the study plan in Table 3 for a detailed list of study procedures and assessments to be performed at screening and throughout the study period.

Patients should have provided signed informed consent prior to any study procedure or restriction being applied.

At Visit 1, patients will be screened and evaluated for eligibility to enter the study. The following assessments will be performed, with data being captured in the pCRF:

- Demography (Date of birth, sex, race)
- Vital signs (Blood pressure and pulse)
- Height and weight
- Surgical and medical history (including nicotine and alcohol use)
- Physical examination
- Concomitant medications
- Safety blood samples (Haematology and Clinical Chemistry) and a mid stream urine sample for urinalysis
- FSH and hCG measurement will be included in the Visit 1 safety analysis for female patients
- A 12 lead ECG
- Lung function tests (FEV₁, SVC, FVC, FEF25-75)

Patients will also be provided with their Bronkotest[®] diary card and instructed on how to complete it.

7.2.1 Follow-up procedures

Investigators should refer to the study plan in Table 3 for a detailed list of study procedures and assessments to be performed at the follow up visit (Visit 5). The following assessments will be performed and recorded in the pCRF at this visit:

- Physical examination

- Safety blood samples (Haematology and Clinical Chemistry) and a mid stream urine sample for urinalysis
- Lung function tests (FEV₁, SVC, FVC, FEF25-75)
- Vital signs (Blood pressure and pulse)
- A 12 lead ECG
- Concomitant medications
- Adverse event questioning

In addition, the patients will return their completed Bronkotest[®] diary card and their spontaneous sputum collection for quantitative bacterial culture as detailed in Section 7.3.9.1.

7.3 Safety

It is of the utmost importance that all staff involved in the study are familiar with the content of this section. The principal investigator is responsible for ensuring this.

7.3.1 Definition of adverse events

An adverse event is the development of an undesirable medical condition or the deterioration of a pre-existing medical condition following or during exposure to a pharmaceutical product, whether or not considered causally related to the product. An undesirable medical condition can be symptoms (eg, nausea, chest pain), signs (eg, tachycardia, enlarged liver) or the abnormal results of an investigation (eg, laboratory findings, electrocardiogram). In clinical studies, an AE can include an undesirable medical condition occurring at any time, including run-in or washout periods, even if no study treatment has been administered.

The term AE is used to include both serious and non-serious AEs

7.3.2 Definitions of serious adverse event

A serious adverse event is an AE occurring during any study phase (ie, run-in, treatment, washout, follow-up), that fulfils one or more of the following criteria:

- Results in death
- Is immediately life-threatening
- Requires in-patient hospitalisation or prolongation of existing hospitalisation
- Results in persistent or significant disability or incapacity
- Is a congenital abnormality or birth defect

- Is an important medical event that may jeopardise the patient or may require medical intervention to prevent one of the outcomes listed above.

For reporting purposes, any suspected transmission via a medicinal product of an infectious agent is also considered an SAE and is reported in an expedited manner. Any organism, virus or infectious particle (for example prion protein transmitting Transmissible Spongiform Encephalopathy), pathogenic or non-pathogenic, is considered an infectious agent.

For further guidance on the definition of a SAE, see Appendix B to the Clinical Study Protocol.

7.3.3 Recording of adverse events

Adverse Events will be collected from enrolment (Visit 1) throughout the treatment period and including the follow-up period (up to Visit 5).

Variables

The following variables will be recorded in the CRF for each AE; description of the AE, the date and time (if available) when the AE started and stopped, intensity, whether the AE is serious or not, causality rating (yes or no), action taken with regard to investigational product, AE caused patient to discontinue study and outcome.

- mild (awareness of sign or symptom, but easily tolerated)
- moderate (discomfort sufficient to cause interference with normal activities)
- severe (incapacitating, with inability to perform normal activities)

It is important to distinguish between serious and severe AEs. Severity is a measure of intensity whereas seriousness is defined by the criteria in Section 7.3.2. An AE of severe intensity need not necessarily be considered serious. For example, nausea that persists for several hours may be considered severe nausea, but not a SAE. On the other hand, a stroke that results in only a limited degree of disability may be considered a mild stroke but would be a SAE.

The Investigator will assess causal relationship between Investigational Product and Adverse Events, and answer “yes” or “no” to the question “Do you consider that there is a reasonable possibility that the event may have been caused by the investigational product.

Causal relationship in cases where the disease under study has deteriorated due to lack of effect will be classified as no reasonable possibility.

For SAEs causal relationship will also be assessed for other medication and/or study procedure. Note that for SAEs that could be associated with any study procedure the causal relationship is implied as “yes”.

A guide to the interpretation of the causality question is found in Appendix B to the Clinical Study Protocol.

Adverse Events based on signs and symptoms

All AEs spontaneously reported by the patient or reported in response to the open question from the study personnel: “*Have you had any health problems since the last time you were asked*”, or revealed by observation will be collected and recorded in the CRF. When collecting AEs, the recording of diagnoses is preferred (when possible) to recording a list of signs and symptoms. However, if a diagnosis is known and there are other signs or symptoms that are not generally part of the diagnosis, the diagnosis and each sign or symptom will be recorded separately.

The investigator should review the diary card information to assess if any data constitutes an adverse event (see definition in Section 7.3.1) and should be recorded in the pCRF.

Adverse Events based on examinations and tests

Deterioration as compared to baseline in protocol-mandated laboratory values, vital signs and other safety variables will only be reported as AEs if they fulfil any of the SAE criteria or are the reason for discontinuation of treatment with the investigational product. If a deterioration in a laboratory value/vital sign is associated with clinical signs and symptoms, the sign/symptom will be reported as an AE and the associated laboratory result/vital sign will be considered as additional information. Any new or aggravated clinically relevant abnormal medical finding at a physical examination as compared with the baseline assessment will be reported as an AE.

Clinically relevant deterioration in non-protocol-mandated measurements will be reported as AE(s).

Wherever possible the reporting investigator uses the clinical, rather than the laboratory term (eg, anaemia versus low haemoglobin value).

Follow-up of unresolved adverse events

Any AEs that are unresolved at the patient’s last AE assessment in the study are followed up by the investigator for as long as medically indicated, but without further recording in the CRF. AstraZeneca retains the right to request additional information for any patient with ongoing AE(s)/SAE(s) at the end of the study, if judged necessary.

7.3.4 Reporting of serious adverse events

All SAEs have to be reported, whether or not considered causally related to the investigational product, or to the study procedure(s). All SAEs will be recorded in the CRF. SAEs will be recorded from the time of informed consent.

The investigator and/or Sponsor are responsible for informing the Ethics Committee and/or the Regulatory Authority of the SAE as per local requirements.

For studies in countries implementing the EU Clinical Trials Directive, informing Ethics Committees and Regulatory Authorities will be performed by AstraZeneca. If any SAE occurs in the course of the study, then investigators or other site personnel inform appropriate AstraZeneca representatives immediately but no later than the end of the next business day of when he or she becomes aware of it.

For fatal or life-threatening adverse events where important or relevant information is missing, active follow-up is undertaken immediately. Investigators or other site personnel inform appropriate AstraZeneca representatives of any follow-up information on a previously reported SAE immediately but no later than the end of the next **business day** of when he or she becomes aware of it.

The AstraZeneca representative will advise the Investigator/study site personnel how to proceed.

Investigators or other site personnel send relevant CRF modules by fax to the designated AstraZeneca representative.

If the Clinical Study Serious Adverse Event Report Form is used, then the Investigators or other site personnel fax on the same day the completed form and any other relevant supporting documentation (eg, ECG, laboratory results, autopsy report) and relevant CRF modules to the AstraZeneca representative.

The designated AstraZeneca representative works with the investigator to ensure that all the necessary information is provided to the appropriate AstraZeneca clinical drug safety data entry site within **one business day** for fatal and life threatening events and within **five calendar** days for other SAEs. If the report arrives late in the day, it can be sent the following morning. If the report arrives during a weekend or public holiday, the information is forwarded as early as possible on the first business day following the weekend or holiday. The clock start date is then the next business day.

The reference document for definition of expectedness/listedness is the IB for the AstraZeneca drug.

7.3.5 Laboratory safety assessment

The laboratory parameters to be collected at the scheduled clinic visits are outlined in Table 6.

Blood samples will be analysed at a central laboratory.

Urinalysis will be performed locally at the study site.

The central laboratory will provide all the materials required for blood and urine sampling. Instructions for labeling, storage and shipping will be detailed in the laboratory manual. The central laboratory will also provide up to date reference ranges throughout the study for the management of patient safety.

Clinically relevant deviations from the reference range in the lab values will be handled as outlined in Section 7.3.3.

For blood volumes see Section 8.1.

Table 6 Laboratory Parameters

Haematology (Blood)	Clinical Chemistry (Serum)	Urinalysis (Urine)
Haemoglobin	Creatinine	Protein
Erythrocyte count	Total bilirubin ^d	Glucose
Haematocrit	Alkaline phosphatase	Haemoglobin
Mean Cell Volume (MCV)	Aspartate aminotransferase (AST)	
Mean Cell Haemoglobin (MCH)	Alanine aminotransferase (ALT)	
Mean Cell Haemoglobin Concentration (MCHC)	Albumin	
Platelet count	Potassium	
Leucocyte count (absolute and percentage including Neutrophil, lymphocyte, monocyte, eosinophil and basophil counts)	Calcium, total	
Reticulocyte count	Sodium	
	Cholesterol	
	Triglycerides	
	Urea	
	Gamma Glutamyltransferase (GGT)	
	Creatinine phosphokinase (CPK) ^a	
	Lactate dehydrogenase (LDH)	
	Glucose	
	Free thyroxine (T4) ^b	
	Thyroid stimulating hormone (TSH) ^b	
	Haptoglobin	
	Follicle stimulating hormone (FSH) ^c	
	hCG ^c	

^a If elevated, S-CPK-MB will be analysed (will not be databased)

^b Included at Visit 1 only

^c Included at Visit 1 for female patients only

^d If elevated, unconjugated bilirubin will be analysed (will not be databased)

7.3.6 Physical examination

As detailed in Table 3, a physical examination will be performed at both Visit 1 and 5 by a medically qualified person.

7.3.7 ECG

At Visits 1, 2, 3, 4 and 5, a resting 12 lead ECG will be performed as detailed in Table 3. The ECG will be performed at site according to local procedure.

ECGs will be recorded in the supine position after the patient has rested for 10 minutes. Only overall evaluation by the investigator will be captured in the pCRF. Any abnormalities (including QTc values) should be reviewed by a cardiologist or appropriately qualified physician.

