Table 3 Table of study assessments

Study Visit	1	1a	1b	2	2a	3	3a	3b	4	5¹
Timing	Day -21 to Day -8	Within 7 days of Visit 2 ^a	Within 7 days of Visit 2 ^a	Day 1	Day 7 (±2 days)	Day 14 (±2 days)	Within 7 days of Visit 4 ^a	Within 7 days of Visit 4 ^a	Day 28 (±2 days)	7 days (±2 days) after Visit 4
Detail	Enrolment	Sputum/ Urine	Sputum/ Urine	Start of treatment	Interim visit	Interim visit	Sputum	Sputum	End of treatment	Follow up visit
Concomitant medications recorded	✓	✓	✓	✓	✓	✓	✓	✓	✓	✓
Adverse event questioning		✓	✓	✓	✓	✓	✓	✓	✓	✓
Pharmacogenetics blood sampling ^g				✓						
Return 24 hr urine collection (for desmosine) ^h		✓ ^h	✓ ^h						✓ ^h	
Return 24 hr sputum collection (for weight) ^h		✓ ^h	✓ ^h						✓ ^h	
Randomisation (AZD9668/placebo)				✓						
Waking sputum sample ^{ij}		✓ ^c	✓ ^c	✓ ^c			✓ ^c	✓ ^c	✓ ^c	
2 hr sputum collection ^{ij}		✓	✓	✓ ^c			✓ ^c	✓ ^c	✓ ^c	
1 to 2 hr post-dose sputum sample ^j									✓	

Table 3 Table of study assessments

Study Visit	1	1a	1b	2	2a	3	3a	3b	4	5 ¹
Timing	Day -21 to Day -8	Within 7 days of Visit 2 ^a	Within 7 days of Visit 2 ^a	Day 1	Day 7 (±2 days)	Day 14 (±2 days)	Within 7 days of Visit 4 ^a	Within 7 days of Visit 4 ^a	Day 28 (±2 days)	7 days (±2 days) after Visit 4
Detail	Enrolment	Sputum/ Urine	Sputum/ Urine	Start of treatment	Interim visit	Interim visit	Sputum	Sputum	End of treatment	Follow up visit
Quantitative sputum culture				✓ ^m						✓
AZD9668 PK sample (blood)				✓ ^c					✓ ^c	
Blood sampling for pharmacodynamic markers ^k				✓ ^c					✓ ^c	
St George's Respiratory Questionnaire				✓					✓	

^a Visit 1a should occur at least 24 hours before Visit 1b.

^b The informed consent should be signed before any study-related procedures, restrictions or screening assessments are performed.

^c Pre-dose

^d To include measurement of FSH (menopausal status) and hCG (pregnancy test) in serum for female patients at Visit 1.

^e Pre-dose and 1-2 hours post dose .

^f Issued at Visit 1 and patient should be instructed to bring it to each clinic visit, for review by site staff. The diary card should be completed daily until termination from the study.

^g Sample should be taken any point after randomisation.

^h Patients should be instructed to start 24 hour collection on rising the day before their scheduled visit. They should collect all sputum/urine for the 24 hour period leading to either Visit 1a **or** Visit 1b and Visit 4.

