From the population PK modelling it was identified that the bioavailability of AZD9668 was approximately 90% of that when it was administered in the fasted state. This did not however have any impact upon the dose selection for the subsequent studies therefore it is not necessary for the patients to restrict food around administration of their doses.

All doses will be administered with approximately 100 mL water. There is no requirement to restrict food consumption before or immediately after administration of AZD9668 except for the morning dose on Days 1 and 28 (Visits 2 and 4, respectively) where an ECG is being performed around t_{max} .

Rationale for the optional pharmacogenetics component of the study is included in Appendix D.

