5.4 Withdrawal of patients

5.4.1 Criteria for discontinuation from the study

Patients may be discontinued from study treatment and assessments at any time. Specific reasons for discontinuing a patient are:

- Voluntary discontinuation by the patient who is at any time free to discontinue his/her participation in the study, without prejudice to further treatment
- Risk to patients as judged by the investigator and/or AstraZeneca
- Severe non-compliance to protocol as judged by the investigator and/or AstraZeneca
- Incorrectly enrolled patients
- Patient lost to follow-up
- Non-compliance to study medication (compliance rate of $\leq 80\%$ following drug accountability at Visit 3)
- Change in QTc >60 msec from baseline value or QTc >500 msec, confirmed by repeat ECG
- Withdrawal of informed consent to the use of biological samples **collected as an integral part of the study**, see Section 8.5
- An ALT / AST level $\geq 3 \times \text{ULN}$ (confirmed on repeat sample) or any pattern of liver function test (LFT) abnormalities giving Investigator or AZ cause for concern
- Evidence of haemolysis as evidenced by the following:
 - Reticulocyte count of over 5%, **and**At least two of the following:
 - a drop in haemoglobin below 10.5 g/dL
 - decrease of 25% in haptoglobin. (The value post-dose to be compared with the average of two pre-dose values. The value should also be 15% below LLN).
 - increase of 25% in unconjugated bilirubin or lactate dehydrogenase (LDH). (The value post-dose to be compared with the average of two pre-dose values. The value should also be 15% above ULN).
- A platelet count of below $80 \times 10^9/\text{L}$ confirmed by a repeat test (in the absence of obvious platelet clumping in a peripheral blood film).

Specific reasons for discontinuing a patient from the genetic research are detailed in Appendix D:

- Withdrawal of consent for genetics research. A patient may withdraw from this genetic research at any time, independent of any decision concerning participation in other aspects of the main study described in this protocol. Voluntary discontinuation by the patient will not prejudice further treatment.

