7.3.8 Vital signs

Vital signs (pulse and blood pressure) will be measured at Visits 1, 2, 3, 4 and 5 as detailed in Table 3. After a 5 minute rest in the sitting position, pulse and blood pressure will be recorded using non invasive equipment.

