12. EVALUATION AND CALCULATION OF VARIABLES BY ASTRAZENECA OR DELEGATE

12.1 Calculation or derivation of safety variable(s)

12.1.1 Safety variables

The following safety data will be collected: vital signs, ECG, haematology, clinical chemistry, urinalysis, sputum culture, reported adverse events. Change from baseline (Visit 2) to end of treatment will be calculated for relevant measurements.

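### The pCRF keeps only the investigator's overall ECG evaluation, so evaluations can be tabulated by arm but the planned database cannot give a numeric QTc change against placebo

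*Protocol*

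**What the plan says.** Protocol Section 7.3.7 schedules a resting 12-lead ECG at Visits 1 to 5. On conduct it says: "The ECG will be performed at site according to local procedure". On data capture it says: "Only overall evaluation by the investigator will be captured in the pCRF". Abnormalities, QTc values among them, are to be reviewed by a cardiologist or suitably qualified physician.

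Table 3 (Section 4.1) times the Visit 2 and Visit 4 ECGs as "Pre-dose and 1-2 hours post dose". Section 4.2 explains that patients fast for the morning dose on Days 1 and 28, "where an ECG is being performed around" tmax.

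ECG is a listed variable for the secondary safety objective (Section 3.2, Table 2). Section 12.1.1 lists it among the safety data and adds: "Change from baseline (Visit 2) to end of treatment will be calculated for relevant measurements".

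QTc is used to exclude patients (Section 5.2, criterion 7) and to stop treatment (Section 5.4.1): "Change in QTc >60 msec from baseline value or QTc >500 msec, confirmed by repeat ECG".

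**The concern.** The trial takes ECGs at the times best suited to showing a drug effect on repolarisation, with a placebo arm and a pre-dose reference, and then enters no interval from them. QTc is also the ECG quantity on which the protocol bases exclusion and stopping. Section 2.1 reports slight QT prolongation (9%) in dogs at a high dose. Section 2.4 says the study is meant to add safety data before the COPD studies.

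What is at stake is one estimate: the difference between AZD9668 and placebo in mean QTc change, with an interval to bound it. This cannot be left to the statistical analysis plan, because such a plan can only summarise data that are collected, and Section 7.3.7 fixes the collection.

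**Working it through.** The protocol states no figure on this point, so there is none to reproduce. The check has two parts.

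**1. Could a QTc value reach the database by another route?**

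- *ECG form.* Section 7.3.7 limits it to the overall evaluation. No section provides for central reading.
- *Adverse events.* Section 7.3.3 restricts when a worsening found on a scheduled test counts as an event. It says that "other safety variables will only be reported as AEs if they fulfil any of the SAE criteria or are the reason for discontinuation". If there are symptoms, the symptom is the reported event. A symptomless QTc rise below the stopping limits would not normally become an adverse event.
- *Overall evaluation.* This is stored and can be compared between arms. Criterion 7 in Section 5.2 counts QTc above 450 msec (men) or 470 msec (women) among ECG abnormalities, so a value well below the 500 msec stop may be marked abnormal. A shift that stays below those values need not be. For illustration, a man moving from an assumed 400 to 420 msec is still under 450.
- *Vital signs.* Pulse cannot stand in for ECG heart rate in a later correction: "After a 5 minute rest in the sitting position, pulse and blood pressure will be recorded", whereas the ECG is taken supine after 10 minutes.
- *Source records.* Section 10.3 gives monitors access to originals, so tracings could be retrieved, but no section plans it.

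The database will therefore hold a categorical ECG result by arm and visit, and no numeric QTc change.

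**2. What would stored values give?**

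Inputs: 20 patients per arm (Section 13.3); 90% two-sided intervals and p<0.1, borrowed from the convention in Section 13.2; SD of individual QTc change 10 to 20 msec, which is an **assumption** not found in the protocol. No covariate adjustment is made.

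Half-width = t(0.95, 38) × SD × √(2/20) = 1.686 × SD × 0.316

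| Assumed SD (msec) | 90% CI half-width (msec) |
|---|---|
| 10 | 5.3 |
| 15 | 8.0 |
| 20 | 10.7 |

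With the normal quantile in place of t, these are 5.2, 7.8 and 10.4.

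Power at two-sided 0.1 (noncentral t, 20 per arm, one time point):

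| True difference (msec) | SD 10 | SD 20 |
|---|---|---|
| 20 | >0.999 | 0.928 |
| 10 | 0.928 | 0.464 |

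**Data burden.** ECGs per completing patient: Visit 1, one; Visit 2, two; Visit 3, one; Visit 4, two; Visit 5, one; total 7. Two fields each gives 7 × 2 = 14 values per patient, and 14 × 40 = 560 for 40 patients.

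**The case against.** The strongest reply is that this is an explicit and proportionate choice for a 40-patient, 28-day exploratory study. No objective asks for a QTc estimate. The dog finding was at plasma levels clearly above the expected human range, and Section 2.1 reports no QT prolongation in the first-in-man study. Locally run ECGs are noisy: at an SD of 20 msec, power for a 10 msec difference is only 46%. All of this stands, and it limits the weight of the point.

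Four stronger readings are tempting, and the protocol does not support them.

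- *That Section 7.3.7 contradicts Section 12.1.1.* The latter plans changes only for relevant measurements, and a categorical evaluation need not be one. The two sections can both be followed.
- *That only patients who cross a stopping limit would be seen.* The overall evaluations are captured for scheduled ECGs and can be tabulated by arm, so the count of stopped patients is not all the trial would show.
- *That the values are destroyed.* They are not entered in the database. The ECGs are done at site, and original records are open to monitors.
- *That the predicted exposure margins (2.6-fold for Cmax, 1.4-fold for AUC, Section 4.2) measure distance from the QT signal.* They are margins to limits based on the rat no-adverse-effect level. They say nothing direct about the dog QT finding, in either direction.

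What the reply does not remove is the capture limit itself. The values will have been available at the site, and the planned database cannot supply a QTc difference at any precision.

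**Conclusion.** The point holds as a limit on a secondary safety summary. Evaluations can be compared between arms; a numeric QTc change, and hence a placebo-controlled estimate, cannot be derived from the planned database. The capture limit is certain from the text. The gain from storing values, a half-width of about 5 to 11 msec, rests on the assumed SD of 10 to 20 msec and 20 evaluable patients per arm, and is likely to sit towards the wide end with local machines.

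A reader might infer that patients are less well protected. The protocol does not support that: sites can apply the change and absolute QTc limits from their own recordings, and abnormal values go to a qualified physician. Eligibility, the stopping rules and the primary analysis are untouched. The point is minor to moderate and worth acting on because the remedy is cheap.

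**What to change.** In Section 7.3.7 and the pCRF, record QT and heart rate (or RR) from every scheduled ECG, alongside the overall evaluation. Take heart rate from the ECG itself. Derive QTc by one stated formula. Summarise change from the Visit 2 pre-dose value by treatment and time point, with a 90% confidence interval for the difference, and name QTc in Section 12.1.1 as one of the measurements for which change is calculated.

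The cost is about 14 extra values per completing patient, roughly 560 in all, with their entry and verification. No extra ECG, visit or blood sample is needed. The drawback is between-site noise from unstandardised local machines, which the report should acknowledge. Doing this prospectively is simpler than collecting tracings afterwards from about 10 centres.
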